9.3 STANDARD TREATMENT

Standard therapy is an antihistamine chosen by the Investigator based on the clinical features of each patient and is to be used for 4 weeks (Period I) by patients of both treatment groups.

9.4 METHOD OF ASSIGNING PATIENTS TO TREATMENT GROUP

For Period I, patients will be randomized with a 1:1 ratio to one of the two treatments (oral Lertal[®] tablets +standard therapy or placebo tablets + standard therapy).

The study product and placebo will be provided in identical boxes and will be identified with a four-digit box number.

The randomization list will be stratified by type of allergy and generated according to permuted blocks codes by an independent statistician through a validated SAS program[®] Software Version 9.4.

The randomization process will be centralized and the assignment to one of the treatments will be carried out through the web-based Electronic Case Report Form (eCRF) system by designated site personnel. When a patient is considered eligible (i.e. he/she fulfils all the inclusion criteria and does not present any exclusion criteria of the Study Protocol), site personnel will access the system in a dedicated section, using a personal account to receive the box number for the incoming patient and will confirm the assignment into the system. Each box number is linked to a treatment code through the randomization list.

A randomized patient is defined as a patient who is registered and is assigned to a box number by the eCRF.

To ensure an adequate number of patients with both types of allergies (pollen and dust mites), the enrollment of patients with dust mite allergies will be blocked should these patients represent 60% of the study population before spring 2018.

9.5 BLINDING PROCEDURES

9.5.1 Methods of blinding

Patients, investigator staff, personnel performing the study assessments and data analysts will remain blinded to the identity of the treatment from the time of randomization until the end of Period I using the following methods:

1. The two treatments will be identical in packaging, labeling, administration schedule, appearance, taste and odor.
2. Randomization data will be kept strictly confidential until the time of unblinding and will not be accessible by anyone involved in the study.

Unblinding will occur only in case of patient emergencies and at the end of Period I. Health authorities will be granted access to unblinded data if needed.

9.5.2 Randomization code breaking during the study

In case of an adverse event (AE), the code should only be broken in circumstances when knowledge of the treatment is required for treating the patient.

The code can be broken at any time through the eCRF system. If the blind is broken, the Investigator should document the date, time of day, and reason for code breaking.

Any patient whose treatment code has been broken inadvertently or for any non-emergency reason will be discontinued from the trial.

9.6 PACKAGING AND LABELING

Each box of Lertal[®] (and placebo) contains 2 foil blisters each containing 15 tablets. The content of the labeling will be in accordance with local regulatory specifications and requirements.

9.7 STORAGE CONDITIONS AND SHELF LIFE

The Principal Investigator or other authorized persons (pharmacists) are responsible for storing the product in a secure and safe place in accordance with local regulations, labeling specifications, policies, and procedures.

9.8 RESPONSIBILITIES

The Investigator, the hospital pharmacist, or other personnel allowed to store and dispense the product will be responsible for ensuring that it is securely maintained as specified by the Sponsor and in accordance with applicable regulatory requirements.

The Investigator will be responsible for ensuring that an accurate record of the product issued and returned is maintained.

Any quality issue detected upon receipt of the product (condition, appearance, documentation, labeling, expiration date, etc.) should be promptly notified to the Sponsor.

9.9 TREATMENT ACCOUNTABILITY AND COMPLIANCE

Patients will be asked to return all unused tablets at Visit 3 and Visit 4 for Period I and at Visit 5 or 6 for Period II (according to type of allergy). Compliance will be assessed by counting unused tablets. A subject Treatment Accountability Log for dispensed and returned treatment will be kept for each patient.

The Investigator will be responsible for ensuring that an accurate record of the treatment issued and returned is maintained through a Site Treatment Accountability Log. Destruction of all study products (used or unused) shall be carried out following the Sponsor's written authorization.

9.10 RESCUE AND CONCOMITANT MEDICATION

Rescue therapy may be used as needed, and is defined as an increment of standard therapy (increase in dose, frequency of administration or change of antihistamine) in Period I, and as the use of any antihistamine in Period II. The use of rescue treatment will be recorded on the CRF and will be evaluated as efficacy variable.

The following medications are prohibited during the study:

- Systemic or intranasal corticosteroids
- Leukotriene antagonists
- Sodium cromoglycate

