2 ASSESSMENT CHART

2.1 STUDY DESIGN

2.1 ASSESSMENT CHART

Study period	Run-in*		Period I (double-blinded)		Period II (follow-up)	
	V1	V2	V3	V4	V5	V6
Visit	V1	V2	V3	V4	V5	V6
Time (weeks)	-2	0	2	4	8	16
Informed consent	X					
Inclusion/Exclusion criteria	X					
Demography/Medical history	X					
Physical examination	X	X		X	X	X
Randomization		X				
TSS, TNSS, TOSS, TTSS		X	X	X		
VAS		X	X	X		
PRQLQ		X		X	X	X
Incidence, intensity, and duration of exacerbations					X	X
Use of rescue medication			X	X	X	X
Provide/return diary		X	X	X	X	X
Dispensation of double blind treatment		X				
Dispensation of Lertal				X		
Concomitant treatment		X	X	X	X	X
Adverse Event monitoring		X	X	X	X	X
Product accountability			X	X	X	X

* Visit 1 and Visit 2 may take place on the same day.

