8.1 INCLUSION CRITERIA

Each patient must meet all of the following inclusion criteria:

- Age 6 to 12 years
- Male or female
- Diagnosis of allergic rhinoconjunctivitis

- Hypersensitivity to dust mites or pollen confirmed with skin-prick test (wheal and redness, ≥ 3 mm more extended than control) performed in the previous 12 months
- Total Symptoms Score (TSS) ≥ 15 and at least 1 for nasal congestion
- Written informed consent of patient and of parent or legal guardian

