8.2 EXCLUSION CRITERIA

Each patient must meet none of the following exclusion criteria:

- Uncontrolled asthma
- Secondary rhinitis to other causes
- Documented evidence of acute or chronic sinusitis
- Nasal polyps
- Chronic or intermittent use of inhaled, oral, intramuscular, intravenous or topical corticosteroids
- Use of leukotriene antagonists
- Continuous use of antihistamines
- Inadequate washout of drugs:
 - Systemic or intranasal corticosteroids: 1 month
 - Leukotriene antagonists: 1 month
 - Sodium cromoglycate: 2 weeks
 - Systemic or intranasal decongestants: 3 days
 - Cetirizine, fexofenadine, loratadine, desloratadine, hydroxyzine: 5-10 days
- Malformations of the nose, ear or throat
- Upper or lower respiratory tract infection in the last 2 weeks
- Participation in other clinical studies in the last month
- Documented hypersensitivity to the study product or its excipients
- Trip planned outside of the study area

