10 ASSESSMENTS

10.1 EFFICACY ASSESSMENTS

10.1.1 Total Symptom Score

The primary variable of the study is the Total Symptoms score (TSS), a patient-reported evaluation of nine symptoms:

- Nasal symptoms (TNSS): itching, sneezing, rhinorrhea, nasal congestion
- Ocular symptoms (TOSS): itching, hyperemia of conjunctiva, tearing
- Throat symptoms (TTSS): itching, coughing

With the help of their parents, patients will score symptoms on a 4-point scale: 0 = absent or irrelevant, 1 = mild, 2 = moderate, 3 = severe.

TNSS is the sum of the scores of nasal symptoms, TOSS the sum of the scores of ocular symptoms and TTSS the sum of throat symptoms.

TSS is calculated as the sum of TNSS, TOSS and TTSS.

At baseline (Visit 2), Visit 3 and Visit 4, and with the help of a parent, patients are asked to assign a score to the symptoms experienced in the last 12 hours and over the previous two weeks.

The overall TSS score is derived as the mean of the two TSS scores related to the symptoms experienced in the last 12 hours and over the previous two weeks.

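### Decongestants must be washed out at entry but are not restricted in Period I, although nasal congestion is a scored item of the primary endpoint

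*Combined protocol and SAP*

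**What the plan says.** - **Entry.** The washout list in section 8.2 covers five classes: corticosteroids, leukotriene antagonists, cromoglycate, decongestants and named antihistamines. The decongestant line reads "Systemic or intranasal decongestants: 3 days". Section 8.1 requires a TSS of 15 or more and "at least 1 for nasal congestion".
- **On study.** In section 9.10, "The following medications are prohibited during the study" is followed by three classes: systemic or intranasal corticosteroids, leukotriene antagonists and sodium cromoglycate.
- **Antihistamines.** Section 9.3: "Standard therapy is an antihistamine chosen by the Investigator based on the clinical features of each patient". Section 9.10 defines rescue as "an increment of standard therapy (increase in dose, frequency of administration or change of antihistamine) in Period I".
- **Endpoint.** Nasal congestion is one of nine TSS items, each scored 0 to 3 (section 10.1.1). "The overall TSS score is derived as the mean of the two TSS scores related to the symptoms experienced in the last 12 hours"; the second of the two scores has a two-week recall. The assessment chart schedules "TSS, TNSS, TOSS, TTSS" at Visits 2, 3 and 4 only.
- **Recording.** Concomitant medication goes into the diary (10.1.6), is asked about at visits (11.1) and is tabulated by ATC class (13.2.2).

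**The concern.** Section 5 of the protocol names decongestants among the usual treatments of this disease, and every enrolled child has the symptom they treat. The 3-day washout keeps the last-12-hours score at baseline free of them. Nothing does the same at Visits 3 and 4.

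Children whose symptoms are less well controlled have more reason to take a decongestant. If the product works, more of these children are on placebo. Their congestion score then falls for a reason unrelated to randomised treatment, and the between-group difference in TSS change shrinks. The use does not appear in the rescue endpoint either, because rescue in Period I covers antihistamine changes only. The total nasal symptom score, a secondary endpoint with four items, is proportionally more exposed than the nine-item TSS.

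It is also unclear whether the per-protocol set, the only supportive analysis of the primary endpoint, would leave such children out. Section 13.2.1 removes significant violations that could influence the efficacy evaluation, but taking a drug that is not prohibited is not plainly a violation.

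**Working it through.** **Step 1: compare the two lists.**

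| Class | Washout in 8.2 | Status on study |
|---|---|---|
| Systemic or intranasal corticosteroids | 1 month | Prohibited (9.10) |
| Leukotriene antagonists | 1 month | Prohibited (9.10) |
| Sodium cromoglycate | 2 weeks | Prohibited (9.10) |
| Named antihistamines | 5-10 days | Standard and rescue therapy (9.3, 9.10) |
| Systemic or intranasal decongestants | 3 days | Not mentioned |

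The nearest other provision is section 11.2.1, which asks that the selection criteria still be met. It applies only when treatment resumes after a temporary stop.

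**Step 2: reproduce the planned power.** Section 13.1 gives 72 per group, effect size 0.47 and a two-sided 5% t-test. The noncentral t distribution gives power of 80.0%, as stated. At the 80 per group to be enrolled it is 84.0%.

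**Step 3: size the dilution.** The documents give neither a usage rate nor an SD, so the following are assumptions:

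- The SD of TSS change is 4 to 6. The planned difference is then 0.47 × 4 = 1.88 to 0.47 × 6 = 2.82 points.
- The share of children using a decongestant in Period I is 5 to 15 percentage points higher on placebo.
- Overall TSS is the mean of two recall scores, so one step on one item counts 0.5 point if it affects one window and 1 point if it affects both.

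*Occasional use* (only the 12-hour score is affected, and congestion falls 1 to 3 steps): shrinkage = gap × share of users dosing within 12 hours of Visit 4 × 0.5 × steps.

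*Repeated use* (one step lower in both windows): shrinkage = gap × 1 point.

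Diluted effect size = 0.47 − shrinkage / SD.

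| Scenario | Shrinkage (points) | SD | Effect size | Power, 72 per group |
|---|---|---|---|---|
| Occasional, 1 in 5 in window, low | 0.05 × 0.2 × 0.5 × 1 = 0.005 | 6 | 0.4692 | 79.8% |
| Occasional, 1 in 5 in window, high | 0.15 × 0.2 × 0.5 × 3 = 0.045 | 4 | 0.4587 | 78.0% |
| Occasional, half in window, low | 0.05 × 0.5 × 0.5 × 1 = 0.0125 | 6 | 0.4679 | 79.6% |
| Occasional, half in window, high | 0.15 × 0.5 × 0.5 × 3 = 0.1125 | 4 | 0.4419 | 75.0% |
| Repeated, low | 0.05 × 1 = 0.05 | 6 | 0.4617 | 78.6% |
| Repeated, high | 0.15 × 1 = 0.15 | 4 | 0.4325 | 73.2% |

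The difference shrinks by 0.2% to 2.4% with one user in five in the window (0.005/2.82 to 0.045/1.88). With repeated use it shrinks by 1.8% to 8.0% (0.05/2.82 to 0.15/1.88).

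**Step 4: direction.** Period I is blinded and randomised. If the product has no effect, expected decongestant use is the same in both arms, and equal use with equal additive effect leaves the mean difference unchanged. If the product works, symptom-driven use pulls the difference towards zero.

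**The case against.** The strongest reply is that this hardly matters. One item of nine is affected, every driver of the calculation is assumed, and the error is conservative. The ITT set needs only one post-baseline TSS and uses LOCF, so the number analysed may lie between 72 and 80 per group. At 80, the one-in-five occasional scenario stays above 82% and the worst repeated-use case is 77.6%. This stands, and it limits the weight of the point.

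The 3-day washout also protects only half of the baseline score. About 11 of the 14 days in the two-week recall remain open to decongestants, so a ban in Period I would not align baseline and follow-up for that half. This stands too, although the mismatch would be the same in both arms.

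Third, the plan already accepts symptom-driven relief: antihistamine rescue is allowed as needed and the observed TSS is analysed regardless. The sponsor may have meant to permit decongestants as ordinary care. The documents do not show that the omission was an oversight. The difference is that antihistamine rescue is defined and counted as an efficacy variable, while decongestant use is neither.

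Fourth, use is recorded and tabulated, so an imbalance would be visible, and section 13.2.2 defers further analysis detail to a separate SAP that was not supplied. That document might settle how use is handled. It would not by itself restrict use during Period I.

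A reader might also infer a second omission, because section 8.2 excludes "Chronic or intermittent use of inhaled, oral, intramuscular, intravenous or topical corticosteroids" while 9.10 names only systemic and intranasal routes. The documents do not support this. The corticosteroid washout line in 8.2 names the same two routes as 9.10, and the topical wording is in a separate bullet on use at entry.

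**Conclusion.** The gap in the text is real: no section restricts decongestants after entry, and they act on a scored item of the primary endpoint. The likely consequence is small. Occasional use, with one user in five dosing in the 12-hour window, costs about 0 to 2 power points from 80.0%. If half of users dose in that window, the cost is at most about 5. It approaches 7 only with repeated use, a 15-point usage gap and an SD of 4 together. All of this rests on assumed usage gaps, dosing patterns, step sizes and SDs.

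A reader might infer that unrestricted use could manufacture a benefit for the product. The documents do not support that: under blinding the expected effect is dilution, and the Type I error is not inflated. Nor is use hidden, since it is recorded. The point is a cheap improvement, not a threat to the trial's conclusion.

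**What to change.** Add systemic or intranasal decongestants to the prohibited list in section 9.10 for Period I, the only period for which the assessment chart schedules the TSS. Record any use as a protocol deviation and keep the child in the ITT analysis with the observed TSS. Leave the primary t-test and the antihistamine-based rescue endpoint unchanged. A child who needs more relief can have the antihistamine increased or changed, which the rescue endpoint already counts.

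**Cost.** One amendment line, with the approvals that section 17 requires and notice to about 17 sites. No new data field is needed. Investigators lose a little freedom in symptomatic care, and treating an intercurrent cold with a decongestant would become a deviation. Deviations could also remove children from the per-protocol set. If use is higher on placebo, those removals would fall mainly in that arm, so the supportive analysis should be read with that in mind.

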10 ASSESSMENTS

10.1 EFFICACY ASSESSMENTS

10.1.1 Total Symptom Score

The primary variable of the study is the Total Symptoms score (TSS), a patient-reported evaluation of nine symptoms:

- Nasal symptoms (TNSS): itching, sneezing, rhinorrhea, nasal congestion
- Ocular symptoms (TOSS): itching, hyperemia of conjunctiva, tearing
- Throat symptoms (TTSS): itching, coughing

With the help of their parents, patients will score symptoms on a 4-point scale: 0 = absent or irrelevant, 1 = mild, 2 = moderate, 3 = severe.

TNSS is the sum of the scores of nasal symptoms, TOSS the sum of the scores of ocular symptoms and TTSS the sum of throat symptoms.

TSS is calculated as the sum of TNSS, TOSS and TTSS.

At baseline (Visit 2), Visit 3 and Visit 4, and with the help of a parent, patients are asked to assign a score to the symptoms experienced in the last 12 hours and over the previous two weeks.

The overall TSS score is derived as the mean of the two TSS scores related to the symptoms experienced in the last 12 hours and over the previous two weeks.

10.1.2 TNSS, TOSS, TTSS

Total Nasal Symptom Score (TNSS), Total Ocular Symptom Score (TOSS) and Total Throat Symptom Score will be evaluated singularly as described for TSS.

The overall TNSS, TOSS and TTSS scores are derived as the mean of the two TNSS, TOSS and TTSS scores related to the symptoms experienced in the last 12 hours and over the previous two weeks.

10.1.3 Visual Analogue Scale (VAS)

At Visit 2, Visit 3 and Visit 4 (Period I) the patient will be asked to indicate overall system distress on a 100 mm Visual Analogue Scale (VAS) where 0 is equal to no discomfort and 100 the worst possible discomfort.

10.1.4 Pediatric Rhinoconjunctivitis Quality of Life Questionnaire (PRQLQ)

The PRQLQ consists of 23 questions in 5 domains (nasal symptoms, ocular symptoms, practical issues, limitation of activities, other symptoms), that are answered on a 7-point scale (0-6), where 0 represents the absence of problems and 6 the greatest symptom distress. Children will complete the questionnaire at baseline and at the end of Period I (Visit 4) and at the end of Period II (Visit 5 or Visit 6). Since parents often have a poor perception of the problems that their child experiences

as a result of their illness, it should be the child who responds to the questions - never the parent or caregiver. Parents should wait in another room to prevent the child looking to the parent for guidance and to stop the parent telling the child how to respond or challenging the child's own response.

10.1.5 Use of rescue medication

Patients will be asked to report the use of any rescue medication during periods I and II of the study.

10.1.6 Patient diary

Children will be given a diary and asked, together with a parent, to write down any rescue medication/concomitant medications taken, as well as the occurrence of any adverse events. During Period II, the number and duration of any exacerbations (need of an antihistamine medication of any kind, at any dose and of any duration) should be indicated in the diary.

10.2 SAFETY

Safety will be assessed on the incidence of adverse events for each treatment and on physical examinations.

10.2.1 Adverse events

An adverse event (AE) is as any untoward medical occurrence in a patient administered the product and which does not necessarily have to have a causal relationship with the treatment.

A **serious adverse event** (SAE) is any untoward medical occurrence that at any dose:

- Results in death, or
- Is life-threatening, or
- Requires inpatient hospitalization or prolongation of existing hospitalization, or
- Results in persistent or significant disability/incapacity, or
- Is a congenital anomaly/birth defect, or
- Is a medically important event.

Should an SAE occur, the Investigator or any designees must send the signed and dated corresponding SAE form by fax or e-mail within 24 hours to the pharmacovigilance officer whose name, fax number, and e-mail address appear below.

CRO Pharmacovigilance Officer: [name], OPIS s.r.l. Email: [contact] [contact] [contact] [contact]

The Investigator should take appropriate measures to follow all AEs until clinical recovery is complete and laboratory results have returned to normal, or until progression has been stabilized to ensure the safety of the patients. This may imply that observations will continue beyond the last planned visit per protocol, and that additional investigations may be requested by the monitoring team.

10.2.2 Physical examination

A Physical examination of the patient will be performed at both visits of the run-in period (Visit 1 and Visit 2), and at the end of periods I and II (Visit 4 and Visit 5 or 6).

10.3 COMPLIANCE

Patients will be asked to return any unused treatment at Visit 3, Visit 4 and Visit 5 or 6 and adherence to treatment will be evaluated by counting the number of unused tablets.

11 STUDY PROCEDURES

11.1 VISIT SCHEDULE

The visit schedule consists of 6 visits. V1 and V2 (baseline) take place during the run-in period, V3 and V4 during the 4 weeks of Period I, and V5 and V6 (only for patients allergic to dust mites) during the 4 weeks or 12 weeks (only for patients allergic to dust mites) of Period II.

At V1 (Week -2), after having obtained signed informed consent from the patient, the Investigator will gather demographic and medical history data. The Investigator will perform a physical examination and evaluate the patient's eligibility for the study according to the inclusion/exclusion criteria indicated in [Section 8](#).

At V2 (Week 0), each patient will be randomized to one of two treatments (Lertal[®] + standard therapy or placebo + standard therapy) and will be provided with enough product to last until Visit 4. The Investigator will perform a physical examination, and the patient will be asked to complete the patient reported outcomes (TSS, TNSS, TOSS, TTSS, VAS, PRQLQ). The Investigator will also enquire about any adverse events the patient may have experienced and about any concomitant medication the patient may have taken since Visit 1. The patient will be given a diary.

Visit 1 and Visit 2 may be performed on the same day.

V3 (Week 2), V4 (Week 4): The patient will be asked to complete the patient reported outcomes (TSS, TNSS, TOSS, TTSS, PRQLQ, VAS) and the Investigator will also enquire about any adverse events the patient may have experienced and about any rescue/concomitant medication the patient may have taken since the previous visit. A physical exam will be performed at V4. The diary should be returned at these visits for review by the Investigator. The patient should also return unused product at each visit.

V5 (Week 8), V6 (Week 16 – only for patients allergic to dust mites): The patient will be asked to complete the quality of life questionnaire (PRQLQ) and the Investigator will also enquire about any adverse events/exacerbations the patient may have experienced and about any rescue/concomitant medication the patient may have taken since the previous visit. A physical exam will be performed at V5 or V6. The diary should be returned at these visits for review by the Investigator.

See the assessment chart in [Section 2.2](#) for details regarding the visit schedule and assessments and [Section 10](#) for information concerning the assessments.

